8.3. Lost to Follow-Up

A patient will be considered lost to follow-up if he or she repeatedly fails to return for scheduled visits and is unable to be contacted by the study site. Site personnel are expected to make diligent attempts to contact patients who fail to return for a scheduled visit or are otherwise unable to be followed up by the site.

9. Study Assessments and Procedures

Section 2 lists the Schedule of Activities, with the study procedures and their timing (including tolerance limits for timing). Adherence to the study design requirements, including those specified in the Schedule of Activities, is essential and required for study conduct.

Appendix 2 lists the laboratory tests that will be performed for this study.

A summary of the maximum number and volume of invasive samples for all sampling during the study will be provided separately.

Unless otherwise stated in the subsections below, all samples collected for specified laboratory tests will be destroyed within **CCI** of receipt of confirmed test results. Certain samples may be retained for a longer period, if necessary, to comply with applicable laws, regulations, or laboratory certification standards.

9.1. Efficacy Assessments

Efficacy endpoints are found in Table AMBU.2. Secondary efficacy endpoint definitions are found in Table AMBU.5. Additional details are provided below.

Table AMBU.5. Secondary Efficacy Endpoint Definitions in Study AMBU

Endpoint	Definition
Modified Mayo Score (MMS) clinical remission	
 Stool frequency (SF) subscore = 0, or SF = 1, and Rectal bleeding (RB) subscore = 0; and Endoscopic subscore (ES) = 0 or 1 (excluding friability)
MMS clinical response	
 A decrease in the MMS of ≥ 2 points and $\geq 30\%$ decrease from baseline, and A decrease of ≥ 1 point in the RB subscore from baseline or a RB score of 0 or 1
Corticosteroid-free remission without surgery	CCI
Pediatric Ulcerative Colitis Activity Index (PUCAI) clinical remission	
 A PUCAI score of < 10 points
PUCAI clinical response	
 A reduction in baseline PUCAI score of ≥ 20 points
Endoscopic remission	
 ES = 0 or 1 (excluding friability)
Symptomatic remission	
 SF = 0, or SF = 1 with ≥ 1-point decrease from baseline, and RB = 0
Histologic-endoscopic mucosal remission	
 Defined as achieving both histologic remission and endoscopic remission. Histologic remission will be specified in the statistical analysis plan (SAP).
Loss of clinical response	
 Week 12 responders: An increase from the Week 12 Partial Mayo score of CCI (with confirmation of negative C. difficile testing) or Week 12 nonresponders who had extended induction: An increase from the Week 24 Partial Mayo score of CCI (with confirmation of negative C. difficile testing)
Symptomatic response	
 CCI from baseline in the composite clinical endpoint of the sum of SF and RB subscores

9.1.1. Mayo Score

This study utilizes components and permutations of the Mayo score (Schroeder et al. 1987) to assess UC disease activity for the primary and secondary endpoints (see [Appendix 7](#)). **Complete and accurate recording of the Mayo SF and RB subscores by patients or their parent/caregiver in their daily electronic diary is necessary for the success of the study.** Adequate bowel preparation and an endoscopy with adequate visualization of the mucosa will enable calculation of the Mayo ES.

Note: The investigator is responsible for ensuring that study participants receive adequate training on and appropriate understanding of:

- the importance of complete bowel preparation prior to endoscopies/flexible sigmoidoscopies
- how to record “remission/ normal” SF at the beginning of the study
- how to evaluate their UC symptoms and to record them on the CCI diary, and
- the importance of being compliant with the CCI diary recording.

The Mayo score is a composite instrument comprised of the following 4 subscores:

Stool Frequency (SF): The SF subscore is a patient-reported measure. This item reports the number of stools in a CCI, relative to the normal number of stools for that patient in the same period, on a 4-point scale (see Appendix 7). CCI

The total number of stools passed CCI will be recorded by the patient or caregiver in a daily electronic diary. The reference “normal” SF for that patient will be recorded electronically at the screening visit. Normal SF for that patient is based on reported SF when the patient was in remission or reported SF before initial onset of signs and symptoms of UC. Study software will use the patient-reported daily SF and the reference normal SF to automatically calculate the Mayo SF subscore. Further details on the analysis of CCI diary items are contained in the SAP.

Rectal Bleeding (RB): The RB subscore is a patient-reported measure. This item reports the most severe amount of blood passed with stool for a given day, on a 4-point scale (see Appendix 7). The patient or caregiver will record this in a CCI electronic diary.

Endoscopic Subscore (ES): The ES is a physician-reported measure that reports the worst appearance of the mucosa on flexible sigmoidoscopy or colonoscopy, on a 4-point scale (see Appendix 7). Determination of the ES is further detailed in Section 9.1.2. Consistent with current clinical practice and regulatory advice, this study subscore excludes friability from the definition of an ES of 1. Also consistent with best clinical trial practice, endoscopy scores will be determined from blinded central readers. The CCI endoscopy score is collected on paper and CCI) in the eCRF. The entry of the local endoscopy is critical to initiate the blinded central reading process.

Physician’s Global Assessment (PGA): The Physician’s Global Assessment (PGA) is a physician-reported measure that summarizes the investigator’s assessment of the patient’s UC disease activity on a 4-point scale (see Appendix 7). The investigator will record the PGA electronically as source data in the tablet device at appropriate study visits. Consistent with regulatory guidance, the PGA will not be used solely for efficacy assessment in this study.

Each subscore is scored on a 4-point scale, ranging from 0 to 3, to give a maximum Mayo score of 12. The study will use the following permutation of the Mayo score:

- Modified Mayo score (MMS): a sum of the Mayo SF, RB, and ES, giving a maximum MMS of 9
- Partial Mayo score: a sum of the Mayo SF, RB, and PGA, giving a maximum Partial Mayo score of 9

Additional permutations of the Mayo score have been described and may be used in analyzing data from this study.

Observer-reported outcomes will be used in place of patient-reported outcomes for children less than 8 years of age. To maintain consistency in reporting of SF and RB data, the patient's age at baseline will determine whether an observer-reported method (ages 2 through 7 years) or a patient-reported method (ages 8 through 17 years) will be used, irrespective of patient's age at later study visits. Efficacy assessments will be conducted in study population age range for which the scale/instrument was validated.

9.1.2. Endoscopy

Endoscopy will be used to determine the Mayo ES at CCI [REDACTED]
[REDACTED] Site and blinded central reading of endoscopies will be used to determine ES.

A flexible sigmoidoscopy or colonoscopy will be performed on all patients during screening, within CCI [REDACTED] to Visit 2. The endoscopy report and histopathology report (if biopsies are sent to the local histopathology laboratory) must be available in the source documents. Prior to performing the screening endoscopy, investigators should ensure that patients have SF and RB scores that suggest they will meet entry criteria (see Inclusion Criterion [6]) and clinically acceptable laboratory test results, including stool tests that are “negative” for *C. difficile* and other intestinal pathogens (see Inclusion Criterion [11] and Exclusion Criteria [21] and [23] to [26]).

Flexible sigmoidoscopy is generally recommended. However, full colonoscopy may be appropriate in some patients (for example, those with mild-to-moderate pan-colitis). The choice of flexible sigmoidoscopy or full colonoscopy is at the investigator's discretion. Other situations that may warrant a full colonoscopy at screening include:

CCI [REDACTED]

In these patients, the investigator can obtain additional biopsies to surveil for dysplasia at the screening colonoscopy. This screening colonoscopy will be performed according to local guidelines and biopsies will be sent to the local histopathology laboratory. Chromoendoscopy may be an acceptable method of targeting biopsies, if allowed according to local guidelines.

- Patients requiring screening for colorectal cancer, who do not have a current screening colonoscopy according to local guidelines. This may include:
 - Personal history indicating increased colorectal cancer risk, for example, previous adenomatous polyps.
 - Patients with other known risk factors.
- Where, in the opinion of the investigator, a colonoscopy is indicated at screening, for example, to confirm that a recent removal of an adenomatous polyp is complete prior to study enrollment.
- Patients who do not have the report of a completed, full colonoscopy available in source documents.

Patients who undergo colonoscopy at screening do not require a separate flexible sigmoidoscopy.

Patients will undergo a CCI [REDACTED]. The endoscopy report and histopathology report (if biopsies are sent to the local histopathology laboratory) must be available in the source documents. Patients who discontinue the study drug because of pregnancy will not undergo a flexible sigmoidoscopy or full colonoscopy at their ETV.

The endoscopist will be a CCI [REDACTED]. Investigators may delegate endoscopy to other members of the study team. However, all study staff performing endoscopy must CCI [REDACTED] at each endoscopy and it will be recorded in the eCRF.

All endoscopic procedures will be video recorded using a storage medium provided by the sponsor or designee. The video images will be sent for independent central reading. An endoscopy video instruction manual from the central reading laboratory will outline the standard study procedures used to capture and transmit video recordings of endoscopic procedures throughout the study, and the qualifications required of the central reader.

The central readers will determine the centrally-read Mayo ES at each CCI [REDACTED] in a blinded manner, as detailed in the image review charter.

The procedure to address disagreement between the site readers and central readers is detailed in the image review charter. The final Mayo ES will be provided to the site prior to being enrolled at Visit 2 to enable determination of the MMS for eligibility.

9.1.3. Endoscopic Biopsies

A histopathology report supporting the diagnosis of UC must be available in the source documents prior to study enrollment, in order to satisfy Inclusion Criterion [5]. If a histopathology report is not available, the investigator can obtain additional biopsies for this purpose at the screening endoscopy (sent to the local histopathology laboratory).

Biopsies will be obtained at each endoscopy to support assessment of the histopathology endpoints in this study and, where permitted, [CCI]. In rare circumstances, the investigator may consider it unsafe to collect all required biopsies; in this situation, fewer biopsies may be collected so as not to jeopardize patient safety. Biopsies will be sent to the central study laboratory for processing. A detailed biopsy reference guide from the central reading laboratory will provide the number of biopsies to be collected, and outline the procedures to be used for secure specimen transfer, processing, slide preparation, and digitization of slides for histopathologic scoring. These results will not be made available to study sites.

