8.1. Discontinuation from Study Drug

8.1.1. Permanent Discontinuation from Study Drug

Study drug may be permanently discontinued during the study. Patients who discontinue study drug early will undergo early termination procedures, which include an ETV and post-treatment follow-up visits.

The investigator will also complete any AE reporting and follow-up that may be required (if applicable, see Section 9.2).

If a patient's study drug is discontinued before the end of the study, the patient should complete the ETV and post-treatment follow-up period as follows:

- Patients who discontinue investigational product during [redacted] will return for post-treatment follow-up visits (Visits 801 and 802) [redacted] after the end-of-treatment visit.
- Patients who discontinue study drug [redacted] will return for post-treatment follow-up visits (Visits 801 and 802) [redacted] after the end-of-treatment visit.

[figure not shown]
Possible reasons leading to permanent discontinuation of investigational product include the following (list is not exhaustive):

Patient Decision

- The patient or the patient's designee, for example, parents or legal guardian, requests to discontinue investigational product.

[redacted]

[redacted]

Disease Worsening

- The patient requires rescue therapy for exacerbation of UC at doses higher than those specified in the “dose stabilization” inclusion criterion (for example, prednisone **CCI** Inclusion Criterion [9]), or with medications specified in the “prohibited medications” exclusion criterion (for example, IV corticosteroids, infliximab, or IV cyclosporine; Exclusion Criterion [19]) (see also [Appendix 5](#)).

Safety Criteria for Study Drug Discontinuation

- The patient has a diagnosis of any of the following during the study:
 - Cancer other than squamous cell or basal cell carcinoma of the skin
 - Polypoid or non-polypoid dysplasia that is endoscopically visible or invisible
 - Active TB (see Section [9.4.5.2](#))
 - HIV/AIDS
 - Hepatitis B or development of detectable HBV DNA (see Section [9.4.5.4](#))
 - Hepatitis C or development of detectable HCV RNA (see Section [9.4.5.5](#)).
- The patient requires a colectomy during the study.
- The patient has a systemic hypersensitivity event or anaphylaxis to mirikizumab (Section [7.8.3.2](#)). Study drug should be discontinued after a systemic hypersensitivity event or anaphylaxis.

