9.1.8. Histopathology Scoring Instrument

The histopathology instruments that will be used for the evaluation of microscopic inflammation and histopathologic disease activity will be specified in the histopathology charter.

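### Section 9.1.3 gives no route for endoscopically invisible dysplasia noticed in centrally held biopsies to reach the investigator, although Section 8.1.1 lists it as a possible safety reason for stopping study drug

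*Protocol*

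**What the plan says.** Protocol Section 8.1.1, under the safety criteria, applies where "The patient has a diagnosis of any of the following during the study", and one entry is "Polypoid or non-polypoid dysplasia that is endoscopically visible or invisible". The section introduces its reasons as possible and non-exhaustive.

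Section 9.1.3 describes the tissue that the trial collects: "Biopsies will be obtained at each endoscopy to support assessment of the histopathology endpoints in this study". It continues: "Biopsies will be sent to the central study laboratory for processing". After describing slide preparation and digitization for scoring, it closes with "These results will not be made available to study sites". Section 9.1.8 leaves to the histopathology charter the choice of instruments for the "evaluation of microscopic inflammation and histopathologic disease activity will be specified in the histopathology charter".

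Section 9.1.2 covers local pathology. For certain patients having a full colonoscopy at screening it says: "In these patients, the investigator can obtain additional biopsies to surveil for dysplasia at the screening colonoscopy". Those biopsies are read locally. A later paragraph, which goes on to the early termination visit, requires a histopathology report in the source documents only where biopsies were in fact sent to a local laboratory.

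**The concern.** Dysplasia that cannot be seen at endoscopy can be diagnosed only on histology. The protocol chose to name it as a safety reason, yet the on-study tissue it is certain to collect is sent to a laboratory whose results the sites do not receive. If someone examining a Week 12 slide centrally noticed dysplasia, the visible wording provides no way to tell the investigator. The investigator would continue dosing without information that bears directly on a listed safety reason, work-up could be delayed, and the safety record would lack the finding. Week 52 tissue matters too, because patients may continue on drug in the extension study (Sections 5.1 and 7.8.1).

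**Working it through.** The plan states no figure that needs reproducing on this point. The check is a cross-reading of the sections, followed by one count.

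**Routes by which on-study dysplasia could reach the investigator**

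| Route | Source | Available after screening? |
|---|---|---|
| Lesion seen by the site endoscopist | 8.1.1, 9.1.2 | Yes, for visible dysplasia only |
| Biopsies sent to the local laboratory | 9.1.2 | Optional; no visible text requires them |
| Local dysplasia surveillance biopsies | 9.1.2 | Expressly described at the screening colonoscopy only |
| Protocol biopsies at each endoscopy | 9.1.3 | Always taken, held centrally, results withheld |

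1. The 8.1.1 entry depends on a diagnosis, whatever its source. The first two routes can supply one, so the entry is not inoperative.
2. For invisible dysplasia the first route drops out. The second depends on a local decision to send tissue. The third is not described after screening.
3. That leaves the fourth. Here 9.1.3 withholds results, and the visible text makes no exception for a safety finding.
4. The documents do not say whether central readers look for dysplasia. If they do not, the guaranteed tissue does not inform the 8.1.1 entry. If one notices it incidentally, 9.1.3 as worded provides no route to the site. The text is incomplete in either case.

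**Comparison with other information rules in the protocol.** Section 10.3.8.2 restricts interim results but releases them to sites when patient safety requires it. Section 9.4.3 returns centrally analyzed laboratory results to the investigator where appropriate. Section 9.1.3 has no such qualifier, and as the more specific rule it is the one a reader would apply to biopsies. The study is open-label (Section 7.3), so passing on a pathology finding reveals no treatment assignment.

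**Count of endoscopies concerned**
- Patients: about 30 (Protocol Section 5.2).
- On-study time points with histologic endpoints: Weeks 12 and 52 (Protocol Table AMBU.2; SAP Table AMBU.6.5), so 2.
- Upper bound: 30 × 2 = 60 biopsied endoscopies.

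This assumes that every patient completes both. Week 12 nonresponders may discontinue (Section 5.1), so the actual number may be lower. It counts endoscopies at those two time points, not dysplasia findings.

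**The case against.** The strongest reply is that nothing here contradicts anything else. One rule acts on a diagnosis and the other withholds endpoint scores, and a site can follow both. In 9.1.3 the withheld results are mentioned straight after histopathologic scoring, and 9.1.8 describes that scoring as a measure of inflammation and disease activity. The natural reading is that activity scores are withheld. No visible text says that a central reader assesses dysplasia. The histopathology charter and the biopsy reference guide are not available for this review, and either may contain a notification procedure. Parts of 8.1.1, 9.1.2 and 9.1.3 are blacked out as well.

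Much of this stands. A reader might infer that investigators cannot act on the dysplasia entry at all, or that the protocol has them dosing children who meet a mandatory stop. The documents support neither inference. Visible lesions and local biopsies can produce a diagnosis. The list is one of possible reasons, and undiagnosed dysplasia does not yet meet an entry framed as a diagnosis. Reading the local-pathology paragraph of 9.1.2 as covering on-study endoscopies is itself an inference from its position and its reference to early termination, but it is the most natural one.

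What the reply does not answer is the invisible case. An optional local route does not ensure that anyone at the site learns of a finding in tissue held only centrally. If a procedure does exist in the charter, the unqualified sentence in 9.1.3 appears to conflict with it.

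**Conclusion.** The point holds in limited form. For endoscopically invisible dysplasia noticed in tissue held only centrally, the visible protocol gives no route to the investigator, although Section 8.1.1 names that condition as a possible safety reason for stopping study drug. Sections 8.1.1, 9.1.2 and 9.1.3 need to be reconciled.

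The exposure is at most about 60 on-study biopsied endoscopies. The documents give no dysplasia rate, so no expected number of findings can be derived; the event is presumed rare in children. The point is worth acting on because the consequence for an affected child could be serious and the remedy is nearly free.

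The conclusion assumes that the blacked-out text contains no safety exception and that the charter and biopsy guide do not already provide a route. Neither can be verified, so confidence is moderate.

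**What to change.** Keep the histologic activity scores withheld from sites. Qualify the last sentence of Section 9.1.3 so that any incidental finding in the central biopsies that matches a safety reason listed in 8.1.1 is reported promptly to the investigator and the medical monitor. Confirm the same in the histopathology charter, and state there whether central readers record dysplasia. Check that the local-pathology wording in 9.1.2 is consistent with both.

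This changes the flow of information only. It proposes no change to any stopping rule, dose, biopsy or reader. The cost is about one sentence in 9.1.3 and one in the charter, plus an occasional incidental-finding query to handle. If the charter already has such a route, only the wording of 9.1.3 needs to be brought into line.

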9.1.4. Pediatric Ulcerative Colitis Activity Index

The PUCAI (Turner et al. 2007) is a clinician-administered, 6-item questionnaire that measures: abdominal pain; RB; stool consistency; number of stools; nocturnal stools; and activity level (see [Appendix 7](#)). All items are answered as an average over the 'past 2 days'. A total disease activity score is calculated from 0 to 85, with severe: 65-85, moderate: 35-60, mild: 10-30, and none: <10. The clinician will record the patient or caregiver/legal guardian responses for the PUCAI electronically as source data in the tablet device at appropriate visits.

9.1.5. Determination of Responder Status/Loss of Response

At Week 12, patients who achieve an MMS clinical response as defined in [Table AMBU.5](#) may move into the maintenance period.

Week 12 Nonresponders are defined as those that **do not meet** the following criteria:

- A decrease in the MMS of [CCI] from baseline, and
- A decrease of [CCI] in the RB subscore from baseline or a RB score [CCI].

Nonresponding patients may receive extended induction dosing via IV infusion Q4W for 12 weeks as noted in [Table AMBU.4](#).

[CCI]

CCI

9.1.6. Growth and Pubertal Assessments

9.1.6.1. Occipital Head Circumference

Occipital head circumference measurements will be performed on patients less than 3 years of age at baseline. Measurements will be taken at baseline and then approximately Q12W thereafter, until the patient reaches the age of 3 years.

